## 6.6. Interim Analyses and Data Monitoring

An interim analysis will be performed when all randomized subjects for Stage 2a have completed follow-up, through Day  $30 \pm 7$ , or the last study visit for those who withdrew early.

The purpose of the interim analysis will be to select one IV bacteriophage dose with the most favorable benefit to risk profile compared to placebo for further evaluation in Stage 2b. The interim analysis will also serve to exclude proceeding with bacteriophage doses that are associated with safety issues, do not reduce pseudomonal colony counts, or have low conditional power. An independent statistician at the SDCC will report to the Phage Advisory Group. The Phage Advisory Group will make a recommendation to the DMID on the selected dose to be considered for Stage 2b. This will only be a recommendation. Ultimately, DMID will review the recommendation (as well as the DSMB recommendation based on independent review of safety and microbiological activity data) and make the final decision on how to proceed regarding Stage 2b.

The interim analysis will consist of a quantitative evaluation of potential effect sizes and associated precision using predicted intervals and predicted interval plots (PIPs) approach. Predicted intervals for DOOR probability will be calculated under the range of assumptions outlined in Section 8.3.

By relying on prediction intervals, no statistical hypothesis testing is required, and no power is lost at interim analysis [1]. In addition, as supplementary information, (predictive) conditional power will be calculated to quantify the probability of rejecting the null hypothesis at the final analysis under a range of assumptions, which are listed in Section 8.3.

Similar to DOOR, changes in  $\log_{10}$  *P. aeruginosa* colony counts (total and each morphology) in sputum cultures from administration of IV bacteriophages through Day  $8 + 3$ , will be evaluated using PIPs to assess the precision for measuring differences in  $\log_{10}$  CFU/mL count.

The planned sample size (20 subjects per Stage 2b arm) will be reevaluated after completion of Stage 2a. If necessary, the sample size will be increased up to 25 subjects for the two arms in Stage 2b (up to 25 subjects for the placebo arm and up to 25 subjects for the selected bacteriophage dose) to provide the desired precision of estimates.

Details of the interim analysis are provided in Section 8.3.

## 6.7. Multicenter Studies

This is a multicenter study, but randomization is not stratified by site. Data will be pooled across all clinical sites and analyses will not adjust for potential site effects.

## 6.8. Multiple Comparisons/Multiplicity

This exploratory study does not include formal hypothesis testing for any of the primary endpoints, therefore no adjustments for multiple testing are planned.

## 7. STUDY SUBJECTS

### 7.1. Disposition of Subjects

Reasons for screening failures will be summarized in [Table 10](#) for Stage 1, [Table 11](#) for Stage 2a, and [Table 12](#) for Stage 2a and 2b. The number and percentage of subjects who complete the treatment period and study milestones, and of subjects who prematurely discontinue during the same period will be presented by treatment group for the ITT population in [Table 5](#) and for the Safety Population in [Table 6](#). The number and percentage of subjects who complete the treatment period and study milestones, and of subjects who prematurely discontinue during the same period will be presented by site for the screened population in [Table 7](#). Enrolled subjects who were ineligible for inclusion in analysis populations will be summarized by reason for subject exclusion and treatment group in [Table 8](#). A listing of subjects excluded from each analysis population and reason for exclusion will be presented in [Listing 5](#).

Reasons for ET as recorded on the termination pages of the eCRF will be summarized (number and percentage) by treatment groups for the safety population in [Table 13](#). Early terminations or discontinued subjects are presented in [Listing 2](#).

Subject disposition and eligibility for analysis will be summarized in a Consolidated Standards of Reporting Trials (CONSORT) flow diagram ([Figure 3](#) and [Figure 4](#)).

### 7.2. Protocol Deviations

A summary of subject-specific protocol deviations will be presented by the reason for the deviation, the deviation category, and treatment group for all enrolled subjects in Stage 1 in [Table 2](#), Stage 2a in [Table 3](#) and Stage 2a and 2b in [Table 4](#). All subject-specific protocol deviations and non-subject specific protocol deviations will be included in Appendix 3 as data listings ([Listing 3](#) and [Listing 4](#), respectively).

Any missing CFQ-R or CFRSD assessments will not be considered protocol deviations. If an unscheduled study visit occurs, any assessments/procedures that do not occur will not be considered protocol deviations.

## 8. MICROBIOLOGICAL ACTIVITY AND BENEFIT TO RISK PROFILE EVALUATION

All variables in the microbiological activity and benefit to risk profile analyses will be listed by subject. Data will be summarized by treatment group. Continuous variables will be summarized with the number of observations, mean, median, SD, quartiles, minimum, and maximum. Categorical variables will be summarized by number and percent in each category. All microbiological activity and benefit to risk profile analyses will be performed using the ITT population.

This study does not include formal hypothesis testing for any of the primary endpoints, and instead relies on CIs for conclusions of treatment effects.

All microbiological activity and benefit to risk profile tables and figures will compare all subjects receiving placebo to all subjects receiving the selected dose of IV bacteriophage chosen from the interim analysis.

### 8.1. Primary Analysis

#### 8.1.1. Safety Analysis

An event that occurs during the treatment period will be considered a TEAE if it was not present before the first dose of the study product or was present before the first dose of the study product and increased in severity during the treatment period.

The number of Grade 2 or higher TEAEs will be presented by Medical Dictionary for Regulatory Activities (MedDRA®) System Organ Class (SOC), High Level Term (HLT), and Preferred Term (PT) by treatment group in [Table 44](#). Subjects will only be counted once for each SOC and PT. The difference in proportion of the number of subjects with events between the Selected dose IV bacteriophage and placebo arms with the corresponding exact 95% CI will be presented in [Table 45](#). This is a primary endpoint and will be analyzed using the ITT population.

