5.2.2 Subject Replacement

Subjects who withdraw, are withdrawn from this study, or are lost to follow-up after signing the Informed Consent Form (ICF) and after administration of the study product will not be replaced.

Subjects who withdraw, are withdrawn from this study, or are lost to follow-up after signing the ICF, but prior to administration of study product, may be replaced.

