10.5.2 Analysis Sets

Four analysis sets will be considered in the statistical analysis of the study:

1. *Screened Set*: The screened set will consist of all subjects who undergo the Screening Visit and receive a patient identification (PID) number.
2. *Intent-to-treat/Randomized Set*: The intent-to-treat (ITT) set will consist of all randomized subjects regardless of whether or not they received study product or placebo.
3. *Safety Set*: The safety set will consist of all randomized subjects who received at least one dose of study product or placebo. Subjects will be analyzed based on the treatment received.
4. *Pharmacokinetics Set*: The PK set will consist of all randomized subjects who contributed at least two of each a sputum and a blood sample.

On the basis of the ITT principle, all of the primary endpoints will be analyzed on the ITT set.

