10.5.3 Subject Disposition

The number of subjects in two of the study sets (ITT and Safety) will be summarized by groups; the screened set will only be summarized by study center.

Screen failures (i.e., subjects screened but not randomized) and the associated reasons for failure will be tabulated overall. The number and percentage of subjects who complete the treatment period (including Day 30 ± 7 days) and of subjects who prematurely discontinue during the same period will be presented for each group and pooled across groups for the ITT set. The reasons for premature discontinuation as recorded on the termination pages of the eCRF will be summarized (number and percentage) by treatment groups for ITT set.

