**Table 13: Reasons for Early Termination – Safety Population**

Reason for Early Termination	4x10  PFU Dose (N=X)		4x10  PFU Dose (N=X)		4x10  PFU Dose (N=X)		Placebo (N=X)		All Subjects (N=X)	
	n	%	n	%	n	%	n	%	%	n
Stage 1										
Any Reason	x	xx	x	xx	x	xx	-	-	x	xx
Serious adverse event (other than death)	x	xx	x	xx	x	xx	-	-	x	xx
Adverse event, other than serious adverse event	x	xx	x	xx	x	xx	-	-	x	xx
Event of special interest	x	xx	x	xx	x	xx	-	-	x	xx
Lost to follow-up	x	xx	x	xx	x	xx	-	-	x	xx
Protocol deviation	x	xx	x	xx	x	xx	-	-	x	xx
Voluntary withdrawal by subject	x	xx	x	xx	x	xx	-	-	x	xx
Withdrawal by investigator	x	xx	x	xx	x	xx	-	-	x	xx
COVID-19 pandemic	x	xx	x	xx	x	xx	-	-	x	xx
Termination of site by sponsor	x	xx	x	xx	x	xx	-	-	x	xx
Termination of study by sponsor	x	xx	x	xx	x	xx	-	-	x	xx
Death	x	xx	x	xx	x	xx	-	-	x	xx
Enrolled but treatment not administered	x	xx	x	xx	x	xx	-	-	x	xx
Not eligible at enrollment	x	xx	x	xx	x	xx	-	-	x	xx
Became ineligible after enrollment	x	xx	x	xx	x	xx	-	-	x	xx
Other	x	xx	x	xx	x	xx	-	-	x	xx
Stage 2a										
...	x	xx	x	xx	x	xx	x	xx	x	xx
Stage 2a and 2b										
...	x	xx	x	xx	x	xx	x	xx	x	xx

Note: N=Number of subjects in the Safety Population.

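### The primary Grade 2+ TEAE comparison is planned on ITT only, so any randomized but undosed subject dilutes the proportions, and Table 13 is on a different population from the one the protocol names

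*SAP*

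**What the plan says.** **Analysis set for the primary safety endpoint.** Protocol 10.5.2 states that "all of the primary endpoints will be analyzed on the ITT set", and the AE row of Protocol Table 3 agrees. SAP 8.1.1 repeats it for the Grade 2+ TEAE endpoint ("This is a primary endpoint and will be analyzed using the ITT population"), as does SAP 9.3.1. Protocol 10.5.2 defines ITT as "all randomized subjects regardless of whether or not they received study product or placebo", and SAP 6.3.2 adds that it is analyzed by randomized treatment. The Safety Population (SAP 6.3.3) is limited to those who received some study product or placebo and is analyzed by treatment received. SAP 9 makes it the default for safety analyses unless otherwise noted.

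**What counts as an event.** Under SAP 8.1.1 an event is treatment-emergent "if it was not present before the first dose of the study product", or if it was present then and later worsened. Protocol 8.2 starts the safety assessment at administration.

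**Withdrawal before dosing.** Randomization takes place at the Baseline/Dosing Visit, ahead of the infusion (Protocol 6.2 and 10.3.1). Under Protocol 5.2.2, subjects who leave after consent but "prior to administration of study product, may be replaced". Neither document removes a replaced subject from ITT once that subject has been randomized.

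**Reasons for leaving.** Protocol 10.5.3 says the reasons for premature discontinuation "will be summarized (number and percentage) by treatment groups for ITT set". SAP 7.1 says the reasons for early termination "will be summarized (number and percentage) by treatment groups for the safety population", in Table 13. One row of that table is "Enrolled but treatment not administered".

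**The concern.** The primary safety contrast has a denominator that can include people who were never exposed. By the plan's own definition they can only count as having no event, so each one lowers the reported proportion in the arm to which they were randomized. Table 45 is the only planned between-arm difference in Grade 2+ TEAE proportions, and SAP 8 says conclusions about treatment effects rest on confidence intervals. If undosed subjects are unevenly spread, or a subject receives something other than the assigned treatment, the contrast no longer describes exposed subjects.

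Table 13 has a related gap. Protocol 10.5.8 says reasons for withdrawal will be reported and compared qualitatively by arm. On the Safety Population, the summary table for that purpose cannot show anyone who left between randomization and dosing.

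**Working it through.** **Arm sizes.** The plan's figures reproduce. The total is 6 (Stage 1) + 32 (Stage 2a) + 2 × 17 (maximum in Stage 2b) = 72. Per compared arm, 8 + 12 = 20 up to 8 + 17 = 25.

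**Formula.** Let an arm have n dosed subjects, m randomized but undosed subjects, and x dosed subjects with a Grade 2+ TEAE. The Safety Population proportion is x/n. The ITT proportion is x/(n + m), which is x/n multiplied by n/(n + m). The documents give neither m nor an expected event rate, so both are assumptions below.

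| Dosed n | Undosed m | n/(n + m) | Relative reduction | 40% becomes |
|---|---|---|---|---|
| 25 | 1 | 25/26 = 0.962 | 3.8% | 10/26 = 38.5% |
| 25 | 2 | 25/27 = 0.926 | 7.4% | 10/27 = 37.0% |
| 20 | 1 | 20/21 = 0.952 | 4.8% | 8/21 = 38.1% |
| 20 | 2 | 20/22 = 0.909 | 9.1% | 8/22 = 36.4% |

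With m = 0 the factor is 1 and nothing changes. Only the proportions are affected. The number of events reported in Table 44 is the same on either denominator.

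**Between-arm difference.** Assume 8/20 with events on phage and 4/20 on placebo among dosed subjects. The intervals use the Miettinen–Nurminen method named in the Table 45 footnote.

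| Set | Phage | Placebo | Difference in points (95% CI) |
|---|---|---|---|
| Safety Population | 40.0% | 20.0% | 20.0 (−8.9 to 46.2) |
| ITT, 1 undosed in each arm | 38.1% | 19.0% | 19.0 (−8.8 to 44.6) |
| ITT, 1 undosed, phage only | 38.1% | 20.0% | 18.1 (−10.4 to 44.0) |
| ITT, 2 undosed, phage only | 36.4% | 20.0% | 16.4 (−11.7 to 41.9) |
| ITT, 1 undosed, placebo only | 40.0% | 19.0% | 21.0 (−7.4 to 46.8) |

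Equal numbers undosed in equal-sized arms shrink the difference by n/(n + m). Unequal numbers can reduce or increase it.

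A deliberately borderline case shows the most that one subject per arm can do. With 10/20 against 4/20, the Safety Population difference is 30.0 points (0.1 to 55.3). On ITT with 1 undosed in each arm it is 28.6 points (−0.3 to 53.4), so the interval moves from just excluding zero to just including it.

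**Table 13.** No arithmetic is needed. Membership of the Safety Population requires receipt of product or placebo. A row for subjects who were enrolled but not given treatment must therefore be zero in every Stage 2 column. The protocol's ITT basis would allow the row to be filled.

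**The case against.** The strongest objection is that the mechanism may involve nobody. Randomization and a single, directly observed infusion take place at the same Day 1 visit. The replacement rule runs from consent, so it also covers people who leave during screening, who are never randomized and never enter ITT. The SAP addendum on undetectable colony counts refers to 32 subjects in the interim analysis, exactly the planned Stage 2a number. That suggests no surplus of replaced randomized subjects, though it does not prove it. All of this stands and is why the effect is probably small. Against it, the plan does provide for undosed subjects: Table 8 has a reason row for them, and so does Table 13.

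Second, dosed-denominator AE rates are already planned. Tables 48, 51 and 54 are on the Safety Population. Because Protocol 8.1.1 records Grade 1 events only when related, those tables should come close to Grade 2+ rates. This also stands, but none of them gives a between-arm difference.

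Third, ITT is an explicit choice in both documents, in a study without formal hypothesis testing, and changing the set after the unblinded interim review has a cost. That is a fair reason to keep the ITT version and add to it rather than replace it.

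A reader might go further in three ways that the documents do not support:

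- **That replacement causes the dilution.** It needs only a randomized, undosed subject, whether or not a replacement is enrolled.
- **That ITT always favors phage on safety.** The placebo-only row above shows the difference increasing.
- **That the plan conceals why undosed subjects left.** Table 5 shows randomized and treated counts by arm on ITT, Table 8 counts those not treated, and Listing 2 gives each subject's reason with treatment group.

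**Conclusion.** The point holds in a limited form. On the plan's own definitions, the ITT denominators of Tables 44 and 45 can include subjects who cannot have the event, and no Safety Population version of the difference offsets this. It is a design weakness shared by protocol and SAP, not a conflict between them.

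One or two undosed subjects per arm would lower a proportion by about 4% to 9% in relative terms. At an assumed 40% rate that is 1.5 to 3.6 points, set against a confidence interval for the difference of roughly ±27 points at 20 per arm. If everyone randomized was dosed as assigned, the two versions are identical. The undosed counts and event rates are assumptions throughout.

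Table 13 is a separate, plain SAP–protocol mismatch that stands whatever the number undosed. Its practical effect is limited, because the counts and individual reasons are available elsewhere. What is missing is the by-arm summary of reasons that includes withdrawals between randomization and dosing.

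**What to change.** Produce Tables 44 and 45 on the Safety Population by treatment received, alongside the ITT versions, and state in SAP 8.1.1 and 9.3.1 that the safety interpretation rests on the Safety Population versions. Align the wording of Protocol 10.5.2 and the AE row of Protocol Table 3, or record the change in the study report, as the SAP preface allows.

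Run Table 13 on the ITT set by arm, as Protocol 10.5.3 states, and correct SAP 7.1 to match. The row for untreated subjects can then hold the people it is meant for.

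The cost is two repeated tables, one changed table population, and a documented change to the safety analysis set made after the interim review. Keeping the ITT tables in the report lets readers see whether that change made any difference.

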#### 8.1.2. Microbiological Activity Analysis

Changes in *P. aeruginosa* CFU/mL in quantitative sputum cultures through Day  $30 \pm 7$  and the corresponding 95% CI for the change from baseline will be summarized by treatment group in [Table 19](#) and changes in  $\log_{10}$  *P. aeruginosa* CFU/mL will be summarized in [Table 20](#). The difference in  $\log_{10}$ -transformed and original scale mean change in *P. aeruginosa* colony counts between IV bacteriophage and placebo arms, along with the corresponding 95% CIs, will be presented in [Table 21](#). A forest plot of the differences in *P. aeruginosa* colony counts is presented in [Figure 6](#) and a forest plot of the differences in  $\log_{10}$  *P. aeruginosa* colony counts is presented in [Figure 7](#). The area under the curve (AUC) calculated using the trapezoidal rule will be used to summarize  $\log_{10}$  *P. aeruginosa* CFU/mL over time. Linear trapezoidal rule will be used to calculate AUC. Area under the curve will only be calculated for subjects with non-missing colony count data from baseline through Day 30. Area under the curve of  $\log_{10}$  *P. aeruginosa* CFU/mL colony counts by treatment group will be presented in [Table 23](#). The difference in AUC between IV bacteriophage and placebo arms and the corresponding 95% CI will be calculated in [Table 24](#). The 95% CI will be obtained from Welch's t-test.

A boxplot including the median, 25th percentile, and 75th percentile of colony counts over time by treatment group will be presented in [Figure 5](#). A listing of individual colony counts will be presented in [Listing 10](#) and a listing of *P. aeruginosa* morphotypes results will be presented in [Listing 11](#).

